Person-to-person transmission: We will use the CDC definition for influenza transmission that refers to the ability of an influenza virus to spread from one person to another, most commonly through large or small droplets containing influenza virus that are expelled when a sick person is coughing or sneezing.

XI. Statistical Analyses

The primary objective is to precisely estimate the proportion of drug eligible individuals with an influenza diagnosis who initiate treatment within 48 hours. We define precision in terms of the width of a 95% confidence interval. The width of a 95% CI will be less than or equal to $\pm 1.96 \cdot 0.5/\sqrt{n}$ where n is the number of individuals who test positive for flu. With 250 households participating and an attack rate of 25% we expect 63 individuals with confirmed influenza infection. This will give a 95% CI for the proportion initiating treatment of ± 0.12 or less.

The proportion of drug eligible individuals receiving the drug and initiating treatment within 48 hours of symptom onset using home-based self-test and delivery methods will be estimated. Binomial regression with log link will be used to calculate the relative risk of receiving and initiating treatment within 48 hours by demographic and clinical factors, including age, sex, race/ethnicity, symptom types, symptom severity, and duration of symptoms. The RR, 95% confidence intervals and p-values will be reported.

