SFS Statistical Analysis Plan
Household Intervention Study
Last Revised 10/8/19

Applicable to the following UW IRB Study Protocols:

Seattle Flu Study (SFS) **(6181)**

Household Intervention Study **(8200)**

Funding:

Brotman-Baty Institute, University of Washington

Table of Contents

A. STUDY OBJECTIVES AND SUMMARY	3
B. FINAL ANALYSIS PLAN	4
B1. ANALYSIS DATASETS	4
B2. BASELINE TABLES AND STUDY CONDUCT	5
Description of the main tables and statistical analyses	5
Study Accrual	5
Baseline Demographic Characteristics	5
Baseline Behavioral Characteristics	5
Baseline Influenza and Respiratory Illness Symptoms	5
Drug adherence	5
Retention	5
Follow-up	5
B3. SAFETY ANALYSIS	5
B4. ENDPOINT ANALYSIS	5
Primary Analysis	5
Secondary Analyses	5
Additional analyses with Influenza virus infection as the Endpoint	5
Additional analyses with other respiratory infections as Endpoints	5
Sensitivity Analyses	5
C1. INTERIM ANALYSIS PLAN	5
Original plan	5

A. Study Objectives and Summary

Purpose: To evaluate the efficacy of a home-based approach to influenza testing in households in order to shorten the time to diagnosis, antiviral delivery, and antiviral initiation and reduce influenza transmission within the household.

Design: This study is an open cohort intervention study with prospective exposure assessment. It is a pilot study of a home-based approach to influenza infection, utilizing self-test kits and rapid home delivery of baloxavir (BXM). All members of all households must be asymptomatic at enrollment.

Population: Households with at least 3 individuals residing there at least 4 days a week, including at least 2 household members that are eligible to take BXM, will be monitored throughout the influenza season for the onset of a cough.

Expected study size: This study will be conducted in up to 1,000 households in the Seattle, WA area.

Study duration: One influenza season, beginning November 1, 2019 and ending May 1, 2020.

Primary aim: Evaluate whether this home-based strategy leads to a large percentage of influenza-positive individuals initiating antiviral therapy within 48 hours of symptom onset.

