A list of serious adverse events will be presented by shelter and by treatment v. intervention period. As defined in the study protocol, serious adverse events include death, a life-threatening reaction to the study drug (or placebo) or other study procedure, hospitalization, or significant or persistent disability or impairment. The incidence of SAE's (events/person-days of follow-up) will be presented both (1) overall and (2) by case v. non-cases. We will test for a difference in SAE rate between the two study periods (intervention v. control) using an exact Poisson test in R.

Baloxavir-resistant influenza transmission

Evidence of a strong intervention effect causing incidence of baloxavir-resistant influenza strains will be evaluated using linear mixed effects logistic regression. The unit of analysis will be influenza-positive tests, and the outcome will be binary: baloxavir-resistant or not baloxavir-resistant.

B5. Power sample size

Table 1. Sample size calculations: Number of clusters needed per arm for two-group cluster-randomized trial - Household intervention study

Effect size (% reduction in flu incidence)			
Power	0.30	0.40	0.50
0.80	57	84	129
0.90	76	112	172

All calculations above assume an ICC of 0.29, anticipated average (or actual) cluster size of 4, and a 15% transmission rate for flu.

Based on these calculations, an arm size of 250 households should be sufficient to detect a 30% reduction in flu incidence at 90% power.

B6. Endpoint Analyses

Primary Analysis

[figure not shown]
Question: Does this home-based self-test diagnostic tool and rapid treatment intervention lead to a large percentage of influenza-positive individuals initiating antiviral therapy within 48 hours of symptom onset?

Endpoint: Cumulative incidence of influenza virus infection

Measure of Association:
Cumulative Incidence (Attack Rate, Incidence Proportion)

$$\text{Cumulative Incidence} = \frac{\text{Number of participants that successfully initiate antiviral therapy within 48 hours of symptom onset (among participants who have a cough and self-test positive for influenza) during the October 2019-May 2020 influenza season}}{\text{Number of influenza-free participants at risk at } t_0 \text{ (baseline)}}$$

Relevant DAG

Exposure:

Exposed (Treatment) = Participants who develop cough and self-test positive
Unexposed (No treatment) = Participants who develop cough but self-test negative

Outcome:

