Success = Participant initiated on antiviral therapy within 48 hours of symptom onset
Failure = Participant is not initiated on antiviral therapy (**more than 48 hours** after symptom onset *or* participant **never** initiates antiviral therapy)

Table 1. Estimated secondary attack rates for planned 2019-2020 study aim on household transmission dynamics.

The study is being conducted in the Seattle, WA area over one influenza season. The goal is to enroll at least 250 (up to 1,000) households. Of these, 25% are estimated to have an individual in the household diagnosed with influenza based on estimates from previous household studies.^{23, 28-29}

A table for influenza attack rates by household size is provided below.

Household attack rate	Total households enrolled	Primary cases	Secondary cases (mean household size 5)	Secondary cases (mean household size 4)	Secondary cases (mean household size 3)
25%	250	63	45-96	34-72	23-48

20%	250	50	36-76	27-57	18-38
10%	250	25	18-38	14-29	9-19
Mean household size includes case.					
Secondary attack rate 18-38%, secondary cases presented as a range based on these high and low bounds.³⁰⁻³²					

Incidence Density

Using time-specific variables such as date of enrollment, weekly symptom diaries and questionnaires, Incidence Density (ID) will be calculated, defined with the following formula:

Incidence Density =

Number of participants that successfully initiate antiviral therapy within 48 hours of symptom onset (among participants who have a cough and self-test positive for influenza)

Total person-days

Model

The proportion of individuals that 1) test positive and 2) receive and initiate treatment within 48 hours of symptom onset using home-based self-test and delivery methods will be analyzed with a binomial regression GLMM with a log link. The outcome follows a binomial distribution, with the number of successes in a series of n independent Bernoulli trials, where each trial has probability of success p . Successes here are defined as an individual successfully initiated on antiviral therapy within 48 hours of symptom onset using home-based self-test to diagnose influenza and home delivery of antivirals. The model is defined below:

Incidence proportions of influenza will be presented in tables.

A formal statistical comparisons between study periods (control vs. intervention) will be performed using a Wald test of the hypothesis

$H_0: RR=1$

$H_a: RR \neq 1$

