The general form of the model (in matrix notation) is:

$$\mathbf{y} = \log\left(\frac{p}{1-p}\right) = \mathbf{X}\boldsymbol{\beta} + \mathbf{Z}\mathbf{u} + \boldsymbol{\epsilon}$$

Variable	Definition
\mathbf{y}	$N \times 1$ column vector, the outcome variable
\mathbf{X}	$N \times p$ matrix of the p predictor variables
$\boldsymbol{\beta}$	$p \times 1$ column vector of the fixed-effects regression coefficients (the β s)
\mathbf{Z}	$N \times q$ design matrix for the q random effects (the random complement to the fixed \mathbf{X})
\mathbf{u}	$q \times 1$ vector of the random effects (the random complement to the fixed $\boldsymbol{\beta}$)
$\boldsymbol{\epsilon}$	$N \times 1$ column vector of the residuals, that part of \mathbf{y} that is not explained by the model height

where each individual β value represents the change in log-odds of receiving and initiating treatment within 48 hours, that are associated with a particular demographic or clinical risk factor. A one-sided test with $\alpha = .05$ will be used. A table of the estimated Risk Ratios for a one unit increase in each covariate, given the other covariate values will be presented, along with the corresponding 95% confidence intervals, and p-values.

Data cleaning and analysis

All analyses will be performed in R version 3.6.1 using the package 'lme4.'

Secondary Analyses:

Question: How well does the self-test perform in comparison to the gold standard molecular test?

Sensitivity, specificity, PPV and NPV of the self-test will be calculated and compared to the gold standard molecular test. Table 2 (below) presents relevant formulas.

Table 2. Sensitivity, Specificity, PPV, and NPV of the Ellume Self-Test, SFS Household Intervention Study, 2019-2020 influenza season

Test Score	The Truth	
	Has Influenza	Does Not Have Influenza
Positive	True Positives (TP) a	False Positives (FP) b
Negative	False Negatives (FN) c	True Negatives (TN) d

$$\text{Sensitivity} = \frac{TP}{TP+FN} = \frac{a}{a+c} \quad \text{Specificity} = \frac{TN}{TN+FP} = \frac{d}{d+b}$$

$$\text{PPV} = \frac{TP}{TP+FP} = \frac{a}{a+b} \quad \text{NPV} = \frac{TN}{TN+FN} = \frac{d}{d+c}$$

Question: What is the association between influenza infection and: (1) influenza strain (by genetic sequencing) and (2) viral kinetics (maximum titer, duration viral RNA detection)?

Sensitivity analysis

Sensitivity analyses will be performed to explore the uniformity of any treatment effects found in the overall analysis.

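### SAP B5 labels relative risks as percentage reductions, so its claim of 90% power for a 30% reduction with 250 households per arm is wrong; power is about 60%

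*SAP*

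**What the plan says.** SAP section B5 presents a table titled "Number of clusters needed per arm for two-group cluster-randomized trial". Its columns are 0.30, 0.40 and 0.50 under the heading "Effect size (% reduction in flu incidence". The entries are 57, 84 and 129 clusters per arm for 80% power, and 76, 112 and 172 for 90% power. The note beneath reads "All calculations above assume an ICC of 0.29, anticipated average (or actual) cluster size of 4, and a 15% transmission rate for flu". B5 gives no alpha and does not say whether the test is one- or two-sided. It then concludes that "an arm size of 250 households should be sufficient to detect a 30% reduction in flu incidence at 90% power".

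Four other places bear on this:

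- SAP section A includes in the study's purpose to shorten the time to "antiviral initiation and reduce influenza transmission within the household".
- SAP section B6 (Model) says: "A formal statistical comparisons between study periods (control vs. intervention) will be performed using a Wald test of the hypothesis". The alternative printed with it is two-sided (RR not equal to 1).
- Further on, B6 states the only alpha in the SAP, one-sided 0.05, directly after describing the regression coefficients ("associated with a particular demographic or clinical risk factor. A one-sided test with").
- Protocol section XI sizes the study differently: "We define precision in terms of the width of a 95% confidence interval".

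**The concern.** With ICC, cluster size and control risk fixed, a larger reduction needs fewer clusters. The B5 table runs the other way, so the column label cannot be right. The concluding sentence takes the label at face value.

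If the columns are really relative risks, the 0.30 column describes a 70% reduction, and B5 contains no calculation for a 30% reduction at all. A reader would then believe that an incidence comparison has 90% power for a moderate effect when it does not. A null result could be misread as evidence against a 30% effect.

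**Working it through.** **Inputs.** From B5: ICC 0.29, cluster size m = 4, rate 15%, 250 households per arm. Inferred: 15% is the control risk p1, and the table uses two-sided alpha 0.05. No dropout is applied, as in B5.

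**Formula.** Clusters per arm = (z_alpha + z_power)² × [p1(1−p1) + p2(1−p2)] / (p1−p2)² × DE / m. The design effect is DE = 1 + (4−1) × 0.29 = 1.87, so DE/m = 0.4675. For two-sided 0.05, (z_alpha + z_power)² is (1.960 + 0.842)² = 7.849 at 80% power and (1.960 + 1.282)² = 10.507 at 90%.

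**Step 1: reproduce the table.** Reading 0.30 as a relative risk gives p2 = 0.15 × 0.30 = 0.045. The variance sum is 0.1275 + 0.042975 = 0.170475 and the squared difference is 0.105² = 0.011025, a ratio of 15.463. Then 15.463 × 7.849 × 0.4675 = 56.74, and 15.463 × 10.507 × 0.4675 = 75.96. Rounded up, these are the printed 57 and 76. All columns, two-sided 0.05, 80% / 90% power:

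| Column | Printed | Read as relative risk | Read as reduction |
|---|---|---|---|
| 0.30 | 57 / 76 | 56.74 / 75.96 → 57 / 76 | 402 / 538 |
| 0.40 | 84 / 112 | 83.31 / 111.53 → 84 / 112 | 214 / 286 |
| 0.50 | 129 / 172 | 128.43 / 171.93 → 129 / 172 | 129 / 172 |

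The relative-risk reading matches all six cells. The printed label matches only the 0.50 column, where a 50% reduction and a relative risk of 0.50 coincide. At one-sided 0.05 the relative-risk reading gives 45/62, 66/91 and 102/141, and no cell matches under either reading.

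**Step 2: clusters for a true 30% reduction.** p2 = 0.15 × 0.70 = 0.105. The variance sum is 0.1275 + 0.093975 = 0.221475 and the squared difference is 0.045² = 0.002025, a ratio of 109.37.

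- 80% power, two-sided: 109.37 × 7.849 × 0.4675 = 401.3, so 402 per arm.
- 90% power, two-sided: 109.37 × 10.507 × 0.4675 = 537.2, so 538 per arm.
- One-sided 0.05: 317 and 438 per arm.

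**Step 3: power at 250 households per arm.** The effective number per arm is 250 × 4 / 1.87 = 534.8. The standard error is √(0.221475 / 534.8) = 0.02035, and 0.045 / 0.02035 = 2.211.

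- Two-sided: Φ(2.211 − 1.960) = 0.599.
- One-sided: Φ(2.211 − 1.645) = 0.714.

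Pooled variance gives 0.597 and 0.713.

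**Step 4: scale of the error.** The 76 clusters printed for 0.30 at 90% power give 23% (two-sided) or 34% (one-sided) power for a true 30% reduction. With 250 per arm, the smallest reduction detectable at 90% power is about 42.5% two-sided or 39% one-sided.

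**Step 5: other readings.** If 15% were the intervention-arm rate (control 0.15 / 0.70 = 21.4%), two-sided power at 250 per arm would be about 78%, and the table would not reproduce. Ignoring clustering gives 85.5% two-sided and 91.5% one-sided, but B5 says the ICC is included. Neither reading supports the sentence as written.

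**The case against.** The strongest reply is that little depends on B5. The primary aim is a proportion sized by confidence-interval width. Protocol v3.1 (January 2020) is later than the SAP (October 2019) and describes one cohort of 250 households, with no randomised or control arm. B5 therefore describes a trial that is not being run. This stands. It limits the consequence, but it does not make the sentence true; it is a further reason to remove it.

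A second point is that the one-sided figures have weak support. The Wald test in B6 carries a two-sided alternative, the one-sided level is attached to the regression on demographic and clinical factors, and the table matches only two-sided 0.05. This also stands. About 60% is the figure consistent with the table, and 71% is given only because one-sided 0.05 is the sole alpha that the SAP states. The SAP's conflict over sidedness needs settling separately.

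Third, 60% is the power of B5's hypothetical parallel-arm trial, not of the B6 comparison. That comparison is between study periods, and it sits in a model whose defined success is starting treatment within 48 hours. This is correct, and the figure should not be read as the power of that test.

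On the inferred control risk, SAP section C helps: it expects 150 per 1000 in the control period and 120 per 1000 in the intervention period. That supports 15% as the control risk. It also implies an expected reduction of only 20% (1 − 120/150). Treated as proportions, that effect has about 30% (two-sided) or 42% (one-sided) power at 250 per arm.

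**Conclusion.** The concern holds. The B5 columns are relative risks labelled as percentage reductions, and the statement of 90% power for a 30% reduction at 250 households per arm is false. The power is about 60% at two-sided 0.05 and 71% at one-sided 0.05. Reaching 90% takes 538 or 438 households per arm respectively.

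This rests on B5's ICC and cluster size, on 15% as the control risk and on the stated alpha. The exact match of all six cells strongly supports the two inferred inputs. The error should be corrected, but it does not touch the primary estimate or its precision calculation.

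**What to change.** Delete the sentence claiming 90% power for a 30% reduction. Replace it with, for example: *This single-cohort pilot makes no power claim for a reduction in influenza incidence; its size rests on the 95% confidence-interval width in Protocol section XI.*

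If the table is kept as background for a possible two-arm design, head the columns *Relative risk 0.30 / 0.40 / 0.50 (70% / 60% / 50% reduction)*, and state the control risk (15%) and alpha (two-sided 0.05).

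The cost is SAP wording only. No participants are added, and enrolment and the primary analysis do not change; the stated power becomes less favourable. The change does not deal with the other control-versus-intervention text in the SAP (the B6 Wald test, the serious adverse event comparison in B4 and the expected rates in section C), which needs its own reconciliation with the single-cohort design.

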review the participant’s medical information and provide an influenza diagnosis based on clinical judgement. If probable influenza is diagnosed, the 98point6 provider will confirm that antiviral treatment is appropriate. If appropriate, drug eligible study participant will subsequently receive a single dose of BXM delivered to their household via rapid delivery service for therapy initiation within 48 hours of symptom onset. Concurrently, the ill individual will collect a Study Day 0 nasal swab sample that will be mailed back to the laboratory for further testing. Additional nasal swabs will be collected at Study Day 2-3 and Study Day 5-7. If influenza is not diagnosed, the ill individual will provide one self-collected or parent/permanent legal guardian-collected nasal swab specimen that will be mailed back to the laboratory for further testing, and the household will remain enrolled and all study participants in the household will continue to self-monitor for presence of symptoms. Once an eligible study participant receives BXM, no additional household members will be eligible to receive BXM; the household will be able to continue monitoring for onset of symptoms, as well as self-testing and swabbing when symptoms develops, but the household will no longer be able to receive BXM delivery.

Figure 1. Study schema

Symptom Table

Feeling Feverish	Muscle or Body Aches
Headache	Rash
Sore Throat or Itchy/Scratchy Nose	Runny/stuffy nose
Feeling More Tired Than Usual	Muscle or body aches
Nausea or Vomiting	Increased trouble with breathing
Ear Pain or Ear Discharge	Diarrhea

The study is being conducted in the Seattle, WA area over one influenza season. The goal is to have 250 households comply with full study procedures. Of these, 25% are estimated to have an individual in the household diagnosed with influenza based on estimates from previous household studies.^{23, 28-29}

A table for influenza attack rates by household size is provided below.

Household attack rate	Total households enrolled	Primary cases	Secondary cases (mean household size 5)	Secondary cases (mean household size 4)	Secondary cases (mean household size 3)
25%	250	63	45-96	34-72	23-48
20%	250	50	36-76	27-57	18-38
10%	250	25	18-38	14-29	9-19
Mean household size includes case.					
Secondary attack rate 18-38%, secondary cases presented as a range based on these high and low bounds. ³⁰⁻³²					

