The University of Washington is the sponsor of the study which is supported by an anonymous funder who does not have any ownership over the management and conduct of the study, the data, or the rights to publish.

III. Objectives

The objective of the study is to measure the proportion of individuals who are initiated on antiviral therapy within 48 hours of symptom onset using a home-based self-test, followed by a telehealth consultation to diagnose influenza and home delivery of antivirals

Primary Outcome Measures

The primary outcome measure will be the proportion of eligible individuals who initiate antiviral therapy at home within 48 hours of symptom onset utilizing a home-based test and the telehealth app for influenza diagnosis and rapid home-delivery of antivirals. It will be calculated using binomial regression with log link, where the number of drug eligible influenza-diagnosed individuals, defined as the number of individuals eligible to receive BXM with both self-test positive influenza and laboratory-confirmed influenza, reporting administration of the study drug within 48 hours of symptom onset is divided by the total number of drug eligible individuals with both self-test positive influenza and laboratory-confirmed influenza.

Secondary endpoints:

- Proportion of individuals who test positive for influenza using the home-based test within 48 hours of symptom onset
- Proportion of individuals with a positive home-based influenza self-test who have a positive test confirmed by the central laboratory
- Sensitivity and specificity of a self-test compared to a laboratory-based molecular influenza test
- Proportion of individuals who are delivered antivirals within 48 hours of symptom onset
- Proportion of individuals who self-report administration antiviral therapy within 48 hours of symptom onset
- Symptom duration and severity among drug eligible and drug ineligible influenza-positive individuals
- Proportion of families with influenza infection diagnosed within 7 days of an index case (another influenza-positive household member)
- Viral quantity and duration of viral RNA detection among drug eligible and drug ineligible influenza-positive participants
- Proportion of drug ineligible study participants seeking medical care for respiratory illness symptoms
- Proportion of individuals who choose to take a self-test among those who are eligible to take a self-test

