Secondary aim: Determine the social and technical infrastructure that would be required to rapidly detect and interrupt influenza transmission at the household level and to determine whether a home-based self-test and antiviral delivery strategy would be feasible in the context of a pandemic.

Primary Objectives:

P1) To measure the proportion of individuals who are initiated on antiviral therapy within 48 hours of symptom onset using home-based self-test to diagnose influenza and home delivery of antivirals.

Secondary Objectives:

S1) Proportion of individuals who test positive for influenza using the home-based test within 48 hours of symptom onset

S2) Proportion of individuals who are delivered antivirals within 48 hours of symptom onset

S3) Symptom duration and severity among cases and household contacts

S4) Viral titer and duration of viral RNA detection among influenza-positive cases

S5) Cost effectiveness, assessed using health resource utilization and school and work absenteeism

S6) Emergence of antiviral resistance, assessed by genetic sequencing of influenza strains

B. Final Analysis Plan

This section describes the main statistical analyses that will be conducted on enrolled households at DSMB meetings and at the end of the study.

B1. Analysis Datasets

The Primary Dataset will consist of all individuals from enrolled households who enroll in the study, comprised of symptomatic (drug-eligible) individuals.

All eligible and enrolled households will be included in the study unless they meet one or more of the following exclusion criteria:

1. Previous documentation of an influenza infection prior to or during the annual influenza season in any household member prior to enrollment

At the participant level, enrolled individuals meeting any of the following criteria will be excluded from analysis (note: their household may still be eligible, as another eligible member of their household may still enroll):

1. The individual's informed consent is determined to be not valid
2. The individual has been double enrolled in the study. In this case, the individual's data will be used once.
3. No symptom questionnaire is collected.

B2. Variable definitions

[See Tables 1a-c for details]

B3. Baseline Tables and Study Conduct

Description of the main tables and statistical analyses

This section describes the main tables and statistical analyses. Metrics will be updated monthly and presented to the DSMB at each meeting.

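### The SAP's primary formula divides on-time starts by everyone at risk at baseline instead of by influenza cases, and its formal tests compare a control period that neither document defines

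*SAP*

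**What the plan says.** **Denominator.** SAP B6 asks, in effect, how large a share of people with influenza start an antiviral inside 48 hours of onset. It then states "Endpoint: Cumulative incidence of influenza virus infection" and sets on-time starts, among people with cough and a positive self-test, over the "Number of influenza-free participants at risk at" baseline. Under Incidence Density the same numerator sits over total person-days. The Model paragraph describes the outcome as "The proportion of individuals that 1) test positive and 2) receive and initiate treatment within 48 hours of symptom onset", which makes testing positive part of the success instead of a condition for entering the denominator. SAP B1 describes the primary dataset as "comprised of symptomatic (drug-eligible) individuals".

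In Protocol III (Primary Outcome Measures), on-time starts are "divided by the total number of drug eligible individuals with both self-test positive influenza and laboratory-confirmed influenza". Protocol XI bases its precision on the number testing positive, not on everyone enrolled.

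**Comparator.** SAP B6 continues: "A formal statistical comparisons between study periods (control vs. intervention) will be performed using a Wald test of the hypothesis" RR = 1. SAP B4 plans to "test for a difference in SAE rate between the two study periods (intervention v. control", and SAP C gives expected rates of 150 and 120 per 1,000 for the control and intervention periods. SAP B5 sizes a two-arm cluster-randomised trial. Yet SAP A describes an open cohort followed for one influenza season.

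**The concern.** The two documents print different primary measures for one study. The SAP's denominator includes people who never fall ill and household members who cannot receive the drug. Its value is therefore set mainly by how much influenza occurs, and only secondarily by how well testing, telehealth and delivery perform. A programme that reached every case would still report a single-digit percentage against a hypothesis of a large one.

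The main formal comparison in B6, and the SAE comparison in B4, need a group of participants or a stretch of time without the intervention. If none exists, these tests have no data to run on. With two ratios and an unexplained test on paper, the headline result is open to choice after the data are seen.

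**Working it through.** **Inputs.** 250 households, 25% attack rate and 63 expected cases (Protocol XI; attack-rate table in Protocol II and SAP B6). Household sizes 3, 4 and 5 (same table); size 4 is also the cluster size in SAP B5. Season 1 November 2019 to 1 May 2020, which is 182 days.

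**1. The protocol's own figure.** 250 × 0.25 = 62.5, rounded to 63. Half-width = 1.96 × 0.5/√63 = 0.1235, which rounds to the stated ±0.12. The protocol's precision is thus built on a case denominator.

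**2. Ceiling of the SAP ratio.** Protocol II says: "Once an eligible study participant receives BXM, no additional household members will be eligible to receive BXM". With 63 affected households there can be at most 63 starts on study-delivered drug. Assuming all members enrol influenza-free:

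| Household size | At risk at baseline | SAP ratio if all 63 start on time | At risk ÷ cases |
|---|---|---|---|
| 3 | 250 × 3 = 750 | 63/750 = 8.4% | 11.9 |
| 4 | 250 × 4 = 1,000 | 63/1,000 = 6.3% | 15.9 |
| 5 | 250 × 5 = 1,250 | 63/1,250 = 5.0% | 19.8 |

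More households, up to the SAP's 1,000, raise numerator and denominator together and leave these ceilings essentially unchanged.

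**3. What drives it.** SAP ratio = (cases ÷ at risk) × (on-time starts ÷ cases). The first factor is an attack rate; only the second is the feasibility question. At size 4, with every case on time, the table's 25%, 20% and 10% attack rates give 63/1,000 = 6.3%, 50/1,000 = 5.0% and 25/1,000 = 2.5%. Performance is perfect in all three. The person-days version behaves the same way: 63/(1,000 × 182) = 0.35 per 1,000 person-days if 1,000 people are followed all season.

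**4. The protocol's proportion.** 63/63 = 100%, if all 63 are drug-eligible and doubly confirmed and later cases in treated households are left out. If the table's secondary cases at size 4 (34 to 72) were all counted, were all drug-eligible and doubly confirmed, and all arose after the household's dose, the same 63 starts would give 63/97 = 64.9% to 63/135 = 46.7%. The protocol does not say which convention applies.

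**5. Precision if fewer cases qualify.** 63 is 25% of 250 households, not a count of drug-eligible, doubly confirmed individuals. The same formula gives 1.96 × 0.5/√50 = 0.139 at n = 50 and 1.96 × 0.5/√25 = 0.196 at n = 25.

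**6. The control period, side by side.** SAP B6, B4 and C name it, and C gives it a rate. None says when it falls, who is in it or what they receive. Protocol II describes one pathway for all households from enrolment to season's end. Protocol XI plans risk ratios by demographic and clinical factors and no contrast of periods. SAP B4 also lists SAEs by shelter, although the study unit is the household, and the software note names the package swCRTdesign. This looks like text from another design, though that is an inference.

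**The case against.** The strongest reply is that the later document already has it right. Protocol version 3.1 (14 January 2020) postdates the SAP (8 October 2019). It prints a case-based numerator and denominator, replaces two-arm power with precision, and drops any contrast of periods. Within the SAP, the B6 question, objective P1 and the success and failure definitions point the same way. B1 defines a dataset, of which a case denominator could be a subset. All of this stands, and it confines the defect to the label, the two printed ratios, the model sentence and the period tests. It does not remove it: neither document says that the protocol prevails, and SAP section B is titled as the final analysis plan.

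A second reply is that the control period may be defined elsewhere. The SAP also covers the wider Seattle Flu Study protocol, which was not available here, and a B6 figure could not be read. This also stands, so the request is to define the period or remove it. The self-test-negative group cannot stand in for it: it is not a period, and the numerator admits only self-test positives, so it scores zero by construction.

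Some stronger readings are tempting but not supported:
- *The primary result is lost.* The data for the protocol's proportion are collected.
- *The SAP ratio would rank seasons wrongly.* The study covers one season, so there is nothing to rank.
- *The protocol's ±0.12 is an error.* 0.1235 rounds to it, and it is the worst case at a proportion of 0.5.
- *The protocol's denominator is settled.* Protocol III requires self-test plus laboratory confirmation, Protocol X uses a provider's clinical diagnosis, and Protocol XI refers to people testing positive.

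**Conclusion.** The point holds. As printed, the SAP's primary ratio cannot exceed about 5.0% to 8.4% with 63 cases, so it cannot show whether a large share of influenza cases start on time, and it conflicts with the protocol's primary outcome. Its denominator is 12 to 20 times the expected number of cases. These figures assume 250 households of 3 to 5 members, all enrolled and influenza-free at baseline, with one treated case per affected household. The contrasting 100% assumes in addition that all 63 are drug-eligible and doubly confirmed and that later household cases are left out.

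The period-based tests cannot be carried out from the two documents available. Whether another protocol supplies a control period is unknown. The fault is in what the SAP instructs, not in the study's ability to estimate its aim, and it should be corrected before the analysis is run.

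**What to change.** 1. **Primary measure.** In SAP B6, replace the endpoint label and formula with the case-based proportion of Protocol III and a 95% CI. Drop the baseline and person-days ratios as primary measures. Bring the model sentence and B1 into line with that denominator.
2. **Case definition.** Reconcile Protocol III, X and XI and carry one definition into the SAP.
3. **Later household cases.** State whether drug-eligible cases arising after a household has already received BXM count in the denominator, and report the other version as a sensitivity analysis. If they count, use a household-cluster-robust interval; otherwise use an exact or Wilson interval, since a Wald interval has zero width when every case starts on time.
4. **Comparator.** Remove the control-versus-intervention tests and language from B6, B4 and C, and the two-arm sample size from B5, for this study. If a control period does exist, state its dates, its participants and what they receive.
5. **Precision.** Use the Protocol XI statement instead, noting that 63 is a count of households with a case. Give half-widths of 0.12 at n = 63, 0.14 at n = 50 and 0.20 at n = 25.

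The cost is a SAP revision plus a short alignment of definitions in the protocol. No new data or participants are needed.
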